2.1. Sample size and justification

A total of 530 residents per group are required to detect an odds ratio of 0.67 for a 4-level ordinal primary outcome (no infection proportion 60%, infection remain in CH 15%, all-cause hospitalisation 10%, all-cause mortality 15%), assuming a two-sided significance level of 5% and 90% statistical power, with no adjustment for clustering [2].

Care homes of varying size will be included, and the number of residents recruited per care home will likely be in the range 20–60. Assuming an intra-cluster correlation of 0.11, a coefficient of variation for care home size of 0.49 (Lothian population analysis in 189 care homes[3]) and an average of 32 residents per care home in the study (assuming that the average number of beds per care home is 40[4] and that not all residents will take part in the study), this gives rise to a design effect or inflation factor of 5.25[5].

Therefore, to compare a single active treatment versus usual care, we will need in the region of 174 care homes, i.e., in excess of 5,500 residents. Allowing for the uncertainty surrounding the parameters listed above (e.g. levels of mortality and transmission rates are expected to be different in the second wave due to improved preparedness, better treatments and the potential impact of the expected vaccination programme, therefore it is possible that the observed proportions in the control group may differ), we propose a sample size of 200 care homes and a total number of residents in the region of 6,400 per comparison, with sample size re-estimation during the trial (once 60-day outcome data are available for at least 75% of residents randomised to standard care).

Therefore, comparing three active (unrelated) treatments concurrently versus standard care (in a 1:1:1:1 allocation ratio) would require 400 care homes in total, corresponding to around 13,000 residents.

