Electronic frailty index at 60 days	Electronic frailty index (eFI) The eFI is presented as a score (e.g. if 9 deficits are present out of a possible total of 36 the FI score = 0.25) - higher scores indicate increasing frailty. The eFI score is used to define frailty categories: - Fit (0 - 0.12) - Mild frailty (> 0.12 - 0.24) - Moderate frailty (> 0.24 - 0.36) - Severe frailty (> 0.36) A composite endpoint strategy will be used to handle the eFI outcome truncated due to death by adding an extra category for death to ensure that death equates to the worst outcome.	-	✓	Ordered categorical	Mixed-effect ordinal logistic regression
Ordinal outcome for the most serious event experienced during the 120 days post- randomisation	Four-level ordinal outcome: No SARS-CoV-2 infection, SARS-CoV-2 infection but resident remains in care home, Admission to hospital, all- cause and Death, all-cause.	✓	✓	Ordered categorical	Mixed-effect ordinal logistic regression
Clinical: care home level					

Page **14** of **25**

Written using WPD 16.5 version 3.0, 13-Sep-2018. Effective date: 13-Oct-2018. Template Author: [name]

Outcome measures	Description	Sourc	es	Type of data	Analysis method
Number of SARS-CoV-2 infections in residents in the care home	Aggregate infection rate in the care home. The numerator will be all confirmed SARS-CoV-2 infections including residents not participating in PROTECT-CH trial and the denominator will be the number of residents in the care home at randomisation.	✓	~	Rate (Proportion)	Linear regression (rate difference) and Poisson regression (rate ratio)
Additional Safety:					
Serious Adverse Reactions (SAR, excluding primary and secondary outcomes) and Suspected Unexpected SAR (SUSAR)		✓			
Adverse events relevant to the intervention as specified in relevant IMP specific appendix to protocol		✓			

*For PEP- only applicable for residents not positive at randomisation; [†]excludes residents with directive for no hospitalisation

Page **15** of **25**

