7. ANALYSIS OF EFFECTIVENESS

The analysis and reporting of the trial will be in accordance with CONSORT guidelines for cluster[7] and adaptive[8] designs. Analyses will be based on pairwise comparisons between each treatment arm and the concurrent standard care arm (reference group). Primary comparative analyses will be based on intention-to-treat principle, with all care homes and residents (eligible for the intervention prior to randomisation) within these care homes analysed according to treatment to which the care home was randomised. All tests will be two-tailed with point estimates and 95% confidence intervals for the treatment effect presented. No formal adjustment for multiple significance testing will be applied [9]. Secondary outcomes will be considered supportive to the primary outcome.

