7.4. Secondary outcomes

Table 1 lists all the secondary outcomes and the type of variables.

Individual-level secondary outcomes will be analysed using mixed-effects regression models appropriate for the type of outcome variable, adjusting for minimisation variables and individual-level factors including age, sex, and vaccination status as fixed effects with a random effect for care home.

Ordered categorical outcomes will be analysed similarly as the primary outcome.

Continuous outcomes will be analysed using linear mixed-effect model, with further adjustment for baseline outcome measure if available. The estimated between group effect will be presented using the adjusted difference between means, along with a 95% confidence interval.

Binary variables will be analysed using mixed effects logistic regression model. The between group effect will be reported using an adjusted risk difference and adjusted risk ratio along with corresponding 95% confidence intervals, obtained using Stata's Margins command with standard errors computed using the delta method.

All-cause mortality (time to death) will be analysed using mixed-effects Cox regression model (shared frailty model). A Kaplan-Meier curve will be presented by trial arm. Other time-to-event outcomes will be analysed using competing-risks survival regression with cluster–robust standard errors. The between group effect will be reported using an adjusted hazard ratio along with a corresponding 95% confidence interval. Estimated cumulative incidence function graphs will be presented for each of the outcomes by trial arm.

The care home level infection rate outcome will be analysed using multiple linear regression of the cluster proportions, adjusted for the cluster-level minimisation variables, to obtain the adjusted difference in mean rates between the intervention and control arms along with the corresponding 95% CI. Poisson regression on cluster-level rates, adjusted for the cluster-level minimisation variables, will be used to obtain estimated rate ratio with corresponding 95% CI. The regression models will be weighted by the inverse of the variance of each cluster summary to take account of variability in cluster size. For this outcome, there will be no adjustment for individual-level covariates since not all residents will have individual level infection data to allow for individual-level analysis.

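### SAP 7.4: the Poisson model for the care-home infection rate ignores between-home variation, and the weighting rule does not define its variance

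*SAP*

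**What the plan says.** The outcome is the proportion of all residents in a home, trial participants or not, with confirmed SARS-CoV-2 infection. According to SAP Table 1, "the denominator will be the number of residents in the care home at randomisation".

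SAP 7.4 specifies two models:
- Rate difference: "The care home level infection rate outcome will be analysed using multiple linear regression of the cluster proportions".
- Rate ratio: "Poisson regression on cluster-level rates, adjusted for the cluster-level minimisation variables, will be used to obtain estimated rate ratio with corresponding 95% CI".

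A further sentence covers both: "The regression models will be weighted by the inverse of the variance of each cluster summary to take account of variability in cluster size". Table 1 lists the same two models.

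For this outcome the SAP gives no formula for the variance, no rule for homes with no infections, and no dispersion parameter, robust standard error or negative binomial alternative. Other outcomes in the same section do have a stated allowance for clustering. Individual-level outcomes get a random effect for care home, and for event times other than death: "Other time-to-event outcomes will be analysed using competing-risks survival regression with cluster–robust standard errors". On status, SAP 7 says: "Secondary outcomes will be considered supportive to the primary outcome".

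**The concern.** A Poisson model takes the variance of a count to equal its mean. Infections within a home are correlated, so home-level counts vary far more than that. SAP 2.1 builds such correlation into the sample size ("Assuming an intra-cluster correlation of 0.11"), although that ICC is for the ordinal primary outcome. Without a correction, the rate-ratio interval reflects only within-home sampling error, and chance differences between homes can be read as treatment effects.

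The weighting sentence is a second problem. The usual sampling variance of a proportion is p(1−p)/n. If each home's observed p is used, a home with no infections has variance zero and no defined weight, and homes with low observed rates get very large weights. In a prophylaxis trial, homes without infections are part of the evidence sought.

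At stake is the only outcome that counts infections among non-participating residents, in a trial with transmission as a secondary objective.

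**Working it through.** **Inputs.** From SAP 2.1: ICC 0.11, CV of home size 0.49, 32 trial residents and 40 beds per home, 200 homes per comparison. Size 40 is used here because all residents count. The planning proportions are 60% uninfected, 15% infected and staying in the home, and 25% with all-cause admission or death, so the infected share lies between 15% and 40%. As a lower anchor, the cohort in Protocol 1.2 had 1,335 infections in 670,628 person-days: 1,335/670,628 × 60 = 0.119, and 1 − exp(−0.119) is about 11% in 60 days.

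**The plan's own figures.** Design effect: 1 + [(0.49² + 1) × 32 − 1] × 0.11 = 5.255 (stated 5.25). Homes: 2 × 530 × 5.25/32 = 173.9 (stated 174). Both reproduce. They concern the primary outcome; the SAP gives no calculation for this one.

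**Step 1: ordinary Poisson.** Fitting rates with weight n is equivalent to fitting counts with a log(n) offset. The true variance of a home's rate is p(1−p)[1+(n−1)ICC]/n, while the model assumes p/n. Averaged over home sizes, the design effect is 1 + [(1 + 0.49²) × 40 − 1] × 0.11 = 6.35. The ratio of true to assumed variance is (1−p) × 6.35, and approximate coverage is 2Φ(1.96 × SE ratio) − 1.

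| Infection risk | Variance ratio | Model SE / true SD | Coverage |
|---|---|---|---|
| 11% | 5.65 | 0.42 | 59% |
| 15% | 5.39 | 0.43 | 60% |
| 25% | 4.76 | 0.46 | 63% |
| 40% | 3.81 | 0.51 | 68% |

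Simulation agrees (200 homes 1:1, beta-binomial counts, gamma home sizes with mean about 40, no covariates, rate ratio 1 or 0.67). SE ratios are 0.41–0.51, coverage is about 56–70%, and type I error is roughly 30–44%. The point estimate is essentially unbiased. Robust standard errors restore coverage to 94–95%.

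Sensitivity to the ICC: at 0.05 the design effect is 1 + 48.604 × 0.05 = 3.43. The variance ratios are then 0.89 × 3.43 = 3.05 at 11% risk and 0.60 × 3.43 = 2.06 at 40%, giving coverage of about 74% and 83%. At 0.25 and 11% risk, simulated coverage is 43–44%.

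**Step 2: Poisson on rates with other weights w and model-based SEs.** The model now assumes variance p/w.

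| Variance used for the weight | Assumed / true variance | Result |
|---|---|---|
| Pooled p with ICC, p(1−p)[1+(n−1)ICC]/n | p, so SE ratio √p: 0.33 at 11%, 0.63 at 40% | Coverage about 44–76% |
| Each home's own p(1−p)/n | depends on the outcome | Coverage about 5–21% |
| [1+(n−1)ICC]/n, without p(1−p) | 1/(1−p) | Conservative, coverage 95–99% |

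The own-rate Poisson variance y/n² does no better: at a true log rate ratio of −0.40 the estimates run from −0.22 to −0.60, with coverage of 10–17%.

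**Step 3: linear model.** Homes with no infections are about 0.3% of homes at 40% risk, 12% at 15% and 21% at 11%. With own-rate weights, zero homes dropped and a rate ratio of 0.67:

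| Control risk | True difference | Mean estimate |
|---|---|---|
| 11% | −0.036 | −0.014 |
| 15% | −0.050 | −0.026 |
| 25% | −0.083 | −0.071 |
| 40% | −0.132 | −0.166 |

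Coverage is 49–78%. Adding 0.5 to avoid zeros does not help (25–76%). With weights n or n/(1+(n−1)ICC), the estimate is unbiased, the SE is 0.90–1.02 of the true SD, and coverage is 92–96%.

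**The case against.** The best defence is that the SAP never prescribes p(1−p)/n with each home's own rate. Its stated purpose, to allow for differing home sizes, fits size- or ICC-based weights, which are finite for every home. Entered in the Poisson fit, n/(1+(n−1)ICC) gives type I error of only 1.1–3.9% in null simulations at 10–40% risk. On that view the text is ambiguous rather than wrong.

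This stands for the linear model and for the zero-infection homes. A reader might infer that the plan drops those homes or that its rate difference is necessarily biased. The documents do not support that, because the variance is undefined.

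It does not rescue the rate ratio. The weight that works is not literally an inverse variance, because it omits p(1−p). It protects the interval only through that unstated scaling. Weight n, or the literal inverse variance with the ICC included, leaves the interval far too short.

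Two further points stand. That standard errors will be model-based is inferred from silence; the analyst may intend robust ones. Also, both agents under consideration are post-exposure (Protocol 1.2), so homes would be randomised after an index case and risk may exceed 11%. The index case can be a staff member, so zeros remain possible, and the interval is too narrow at 40% risk as well.

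**Conclusion.** As written, the rate-ratio analysis makes no allowance for overdispersion. With model-based standard errors its 95% CI covers about 56–70% at risks of 11–40%, and literal inverse-variance weighting does not reliably correct this. The undefined variance is a second gap. It biases the risk difference only if own-rate variances are used, and it affects few homes for lack of a weight when risk is near 40%.

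Three stronger conclusions might be drawn and are not supported:
- That all intervals for this outcome are too narrow. Linear-model intervals are about right under size- or ICC-based weights.
- That this is the main evidence on transmission. SAP 4.2 and 7.5 name time to infection as the transmission-related secondary outcome, and it has cluster-robust standard errors.
- That the trial's main conclusion is at risk. The outcome is supportive, and the primary model has its own random effect for care home.

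Severity: should-fix. The sizes rest on assumptions outside the documents: the ICC of 0.11 applied to infection, beta-binomial counts, gamma home sizes, mean occupancy of about 40, and the 11–40% risk range. The direction holds for any material between-home correlation; even an ICC of 0.05 gives 74–83% coverage by the formula in the working.

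**What to change.** Replace the weighting sentence and the Poisson sentence in SAP 7.4, and amend the matching cell of Table 1:
- Rate difference: regress home proportions with weights n/(1+(n−1)ICC), using one common ICC, or with weights n and robust standard errors.
- Rate ratio: model infection counts with a log link, an offset of log(residents at randomisation) and robust (sandwich) standard errors, or use a negative binomial model.
- State that homes with no infections stay in both analyses, and that no weight depends on a home's own observed rate.

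No new data or design change is needed. The cost is a rate-ratio interval about twice as wide as the ordinary Poisson one (1/0.51 = 2.0 to 1/0.41 = 2.4 times), which is the width the between-home variation requires.

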1.2. Trial Rationale and Risk/Benefit Assessment

Vaccines are intended to and usually prevent symptomatic COVID-19 disease (and in some cases reduce disease severity), however, vaccines may be less effective in older people with immunosenescence so there is an additional need for effective prevention strategies in Care Home residents, a group who are at high risk of infection and poor outcomes.

The case fatality rate (95% CI) for care home residents with COVID-19 during the first wave of the pandemic in 2020 was 35.7% (31.9-39.7%). Importantly care home residents with no direct evidence of infection of COVID-19, were twice as likely to die if their home experienced an outbreak, than if they lived in a home with no COVID-19.³⁰

Coming forward to 2021. The VIVALDI-2 study considered 10,412 residents (median age 86 years) from 310 care homes, 9,160 were vaccinated with either ChAdOx1 (6,138; 67%) or BNT162b2 (3,022; 33%) vaccines. A total of 670,628 person days and 1,335 PCR-positive infections were included. Adjusted hazard ratios (aHRs) for PCR-positive infection relative to unvaccinated residents declined from 28 days following the first vaccine dose to 0.44 (0.24, 0.81) at 28-34 days and 0.38 (0.19, 0.77) at 35-48 days. Similar effect sizes were seen for ChAdOx1 (aHR 0.32 [0.15-0.66] and BNT162b2 (aHR 0.35 [0.17, 0.71]) vaccines at 35-48 days.²⁹

Trial	Prophylactic therapy in care homes trial	Protocol Final v1.0	date:	13-May-2021	Page:	15 of 44
name:	U1111-1265-4068	version:				

Vaccination diminishes the risk of COVID-19 infection for care home residents but does not remove it completely. COVID-19 infection is associated with high mortality for all residents who live in a care home where an outbreak becomes established. If prophylactic therapies can modify the transmission and severity of SARS-CoV-2 infection, then they will be of substantial benefit to residents throughout the care home. Importantly, both agents being considered at present are postexposure prophylaxis. By the time a resident starts taking one of the study medications, they are at increased risk of dying by virtue of exposure.

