5.2. Baseline characteristics

Baseline characteristics for cluster and individual participant levels will be summarised both overall and by treatment groups using appropriate descriptive statistics for continuous (mean, standard deviation, median, lower & upper quartiles, minimum, maximum and number of observations) and categorical (frequency counts and percentages) characteristics to illustrate balance between the groups at baseline. Baseline summaries will be based on the principal comparisons (between each treatment group and the concurrent standard care group respectively).

Cluster-level characteristics will include:

- Minimisation variables
 - care home type (residential vs nursing vs nursing and residential dual registration)
 - prior COVID-19 in care home at any time (yes vs no)
 - size of care home Total number of residents in care home (small (<30 residents), medium (>30, <50 residents), large (>50 residents))
 - care home has capacity to give oxygen (yes vs no)
- Any residents in care home received vaccination against COVID-19
- Any staff in care home received vaccination against COVID-19
- Country
- Care home ownership
- Registered for clients with learning disabilities
- CQC rating (outstanding, good, requires improvement) or equivalent in devolved administrations.
- Time between positive test for COVID-19 in resident/member of staff and care home randomisation (For PEP only)

Individual resident level baseline demographic and clinical characteristics will include:

- Age
- Sex
- Ethnicity
- BMI (from height and weight)
- Advance directive for no hospitalisation
- Do Not Attempt Resuscitation order
- Smoking status
- Co-morbidities (diabetes, heart disease, chronic lung disease, severe liver disease, severe kidney impairment, dementia, stroke)
- Previous positive test for COVID-19
- Tested positive for COVID-19 at randomisation (For PEP only)
- Received vaccination for COVID-19
- Time in care home
- Electronic frailty index
- Type of consent

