7.1. Primary analysis

Primary between-group comparison will be based on individual-level data rather than cluster-level summaries. Primary comparative analyses will employ a multi-level mixed-effects ordinal logistic regression model to reflect the ordinal nature of the primary outcome and allow for the betweencluster variation (clustering within care homes). A random intercept model will be fitted. The model will adjust for all the cluster-level minimisation factors and individual-level factors including age, sex, and vaccination status (ordinal: no vaccination, partial dose, full dose) as fixed effects. These individual-level factors have been shown to contribute to disparities in fatality rates in COVID-19 patients. The treatment comparison will be presented as an adjusted common proportional odds ratio together with 95% confidence interval, and p-value.

The ordinal logistic regression model is based on the proportionality of odds (parallel lines) assumption, that is, the treatment effect is consistent across the whole composite ordinal primary outcome spectrum. We will test for non-proportionality using a Likelihood Ratio test comparing the model where the coefficients are constrained to be equal across the three log-odds contrasts and the model where the proportional odds assumption is relaxed. If the data sets show significant departures from the proportionality assumption, then an extension of the multilevel ordinal logistic regression model to allow for non-proportional odds will be employed.

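### The care-home-level infection analysis leaves out vaccination coverage for a reason that does not exclude it; the cost is precision only, and probably small

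*SAP*

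**What the plan says.** SAP Table 1 (section 2.4) defines the outcome over everyone living in the home: "The numerator will be all confirmed SARS-CoV-2 infections including residents not participating in PROTECT-CH trial". Each home's count is divided by how many people lived there when it was randomised. Under SAP 4.2 the analysis set includes residents who did not consent.

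For the linear model, SAP 7.4 says that the home proportions are "adjusted for the cluster-level minimisation variables, to obtain the adjusted difference in mean rates between the intervention and control arms". The Poisson model for the rate ratio has the same covariates. The reason for stopping there is: "For this outcome, there will be no adjustment for individual-level covariates since not all residents will have individual level infection data". The sentence goes on to say that such data would be needed for an analysis at individual level.

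For the individual-level secondary outcomes, the same section specifies "adjusting for minimisation variables and individual-level factors including age, sex, and vaccination status as fixed effects". The primary model in SAP 7.1 likewise includes "individual-level factors including age, sex, and vaccination status", with vaccination in three levels (none, partial, full). SAP 5.2 lists receipt of vaccination as a baseline item for each resident. Protocol 6.2 says that allocation is revealed only after consent and baseline data collection.

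**The concern.** The stated reason concerns the outcome data, but the decision concerns covariates. Without individual infection results for non-participants, no individual-level model can be fitted to all residents. The planned models, however, are regressions on one summary per home, and the share of a home's consented residents who were vaccinated is also one number per home. It can be derived from data the trial already holds, and it is fixed before randomisation.

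Precision is at stake. This is the only outcome that includes residents outside the trial, and it rests on about 100 homes per arm. If coverage varies between homes and predicts infection, leaving it out makes the interval wider than it need be. Adding it later, after seeing an imbalance, would be post hoc: the provision in SAP 7.2 for imbalanced covariates covers the primary outcome only.

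**Working it through.** **What the plan's figures give.** The documents state no power or precision for this outcome, so there is no figure to reproduce for it. The inputs borrowed from the primary sample size (SAP 2.1, Protocol 13.1) do reproduce. The design effect is 1 + ((0.49² + 1) × 32 − 1) × 0.11 = 5.255, against 5.25 stated. Homes needed are 2 × 530 × 5.255 / 32 = 174.1, against 174 stated.

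**Inputs from the documents.**
- 200 homes per comparison, so 100 per arm; 40 beds and 32 participants per home; ICC 0.11.
- Coverage (Protocol 1.2): "The VIVALDI-2 study considered 10,412 residents (median age 86 years) from 310 care homes, 9,160 were vaccinated", so 9,160 / 10,412 = 0.8798.
- Vaccine effect (Protocol 1.2): adjusted hazard ratio 0.38 (0.19 to 0.77) at 35-48 days after the first dose.
- Infection risk: the same cohort had 1,335 infections in 670,628 person-days, and 1,335 / 670,628 × 60 = 0.119, about 12% per 60 days. Homes randomised on an index case could be higher. The planned category proportions allow 15% (infected and remaining in the home) up to 40% (everyone outside the no-infection category, which counts every all-cause admission and death as infected).

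**Assumptions.** The between-home SD of coverage is not in the documents; I use 5, 10 and 15 percentage points. The ICC is carried over from the ordinal outcome, and the hazard ratio is treated as a risk ratio. Homes are taken as equal in size (40 residents) and weight. The minimisation factors are taken to absorb none of the coverage effect.

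**Formulas** for risk p, hazard ratio HR and SD of coverage s:
- Variance of a home's proportion: v = p(1 − p)[0.11 + 0.89/40].
- Risk if unvaccinated: p0 = p / (1 − (1 − HR) × 0.8798).
- Slope on coverage: b = p0(1 − HR).
- Share of variance explained: R² = (b × s)² / v.
- Standard error of the difference: √(2v(1 − R²)/100).

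**Worked case: p = 0.25, s = 0.10, HR = 0.38.**
- v = 0.1875 × 0.13225 = 0.0248.
- p0 = 0.25 / 0.4546 = 0.550, and b = 0.550 × 0.62 = 0.341.
- R² = 0.0341² / 0.0248 = 4.7%.
- The standard error falls by 1 − √(1 − 0.047) = 2.4%. The 95% half-width goes from 4.36 to 4.26 percentage points.

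**R² over the range, HR 0.38 (reduction in standard error in brackets).**

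| Infection risk | SD 5 points | SD 10 points | SD 15 points |
|---|---|---|---|
| 12% | 0.5% (0.2%) | 1.9% (1.0%) | 4.3% (2.2%) |
| 15% | 0.6% (0.3%) | 2.5% (1.3%) | 5.6% (2.8%) |
| 25% | 1.2% (0.6%) | 4.7% (2.4%) | 10.6% (5.4%) |
| 40% | 2.3% (1.2%) | 9.4% (4.8%) | 21.1% (11.2%) |

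**Coverage seen in participants only.** With 32 of 40 residents observed, the sampling variance of coverage is 0.8798 × 0.1202 / 32 × (1 − 32/40) = 0.00066. Reliability at s = 0.10 is 0.01 / 0.01066 = 0.938, so R² in the worked case falls from 4.7% to 4.4%. This treats participants as a random sample of the home.

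**Sensitivity to the hazard ratio.** At p = 0.25 and s = 0.10, the limits of its interval give R² of 0.2% (HR 0.77) and about 20% (HR 0.19).

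These figures are for the linear model; the Poisson model was not calculated.

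**The case against.** The strongest reply is that the SAP sentence is true as written: individual-level covariates belong in an individual-level analysis, and none is possible here. The residents without individual infection data also have no listed individual covariates, so a participant summary is only a proxy for the whole home. That stands, but it does not answer the point. A home-level proxy fixed before randomisation is a legitimate covariate; its imperfection reduces the gain and cannot bias the comparison.

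The outcome's importance should also not be inflated. SAP 4.2 and 7.5 name time to infection as the transmission-related secondary outcome, and that one is adjusted for vaccination. SAP 7 treats all secondary outcomes as supportive.

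Three stronger readings are tempting and unsupported:
- **That the planned estimate is biased, or unadjusted.** Homes are randomised, the minimisation factors stay in the model, and the interval already allows for chance imbalance.
- **That the loss is known to be large.** The upper end of the range needs both a 40% infection risk and an assumed SD of 15 points.
- **That the SAP relies on an inadequate vaccination item.** SAP 5.2 does list "Any residents in care home received vaccination against COVID-19", which at 88% uptake would be yes in almost every home. But it is a descriptive baseline item and is never offered as a covariate.

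**Conclusion.** The point holds as a matter of efficiency. The reason given in SAP 7.4 excludes an individual-level model and nothing more, and a vaccination covariate is available from data already planned. The plan is valid without it, and no stated figure is wrong.

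The gain cannot be fixed from the documents. It runs from under 1% to about 21% of between-home variance over the assumed SDs and risks at a hazard ratio of 0.38. At an SD of 10 points and risk of 12 to 25% it is about 2 to 5%, worth about 1 to 2.4% of the standard error. Any overlap with the minimisation factors would lower it. One spent degree of freedom costs roughly 1/200 = 0.5% of variance, so at the lowest corner of the table there is no net gain.

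Only vaccination coverage has support in the documents. No gain can be derived for mean age. A previous-positive-test summary would overlap the prior COVID-19 minimisation factor, and a staff vaccination count would be new data collection; neither is recommended.

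**What to change.** In SAP 7.4, replace the sentence giving the reason with wording such as: *An individual-level model is not possible because not all residents have individual infection data. Both cluster-level regressions will adjust for the minimisation variables and for the proportion of consented residents in each home who were vaccinated against COVID-19 at baseline.*

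State how the none/partial/full levels are collapsed. The cited effect is for a first dose, so at least one dose matches the evidence available; the documents give no coverage or effect for full vaccination. Participants' mean age may be added for consistency with the other models, but with no claimed gain.

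The cost is SAP wording, made before allocations are seen, and one degree of freedom out of 200 homes (two with mean age). No new data are needed. The report should say that the covariate describes participants and stands in for all residents.
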